10.2.2.6 Study Drug Compliance

Study drug compliance will be summarized based on the OLE-FAS.

Study drug compliance will be calculated as: $100 \times [1 - (\text{total number of days of study drug interruption started before last dose of study drug}) / (\text{duration of study drug exposure in days})]$. A study drug interruption on a given day is defined as an interruption of any study drug dose or component on that day.

Study drug compliance will be summarized descriptively by the number of subjects (n), mean, SD, median, min, and max. It will also be summarized in categories: <80% and $\geq 80\%$ using frequency tables.

In addition, percentage of tablets taken will be calculated using the following formula: $100 \times [(\text{total number of tablets dispensed}) - (\text{total number of tablets returned})] / (\text{total number of tablets planned to be taken per day} \times \text{duration of study drug exposure in days})$. A summary similar to that for study drug compliance will be produced based on the OLE-FAS.

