AE: adverse event; BMI: body mass index; CF: cystic fibrosis; CFQ-R: Cystic Fibrosis Questionnaire-Revised; ETT: Early Termination of Treatment; FE-1: fecal elastase-1; ICF: informed consent form; IRT: immunoreactive trypsinogen; PEx: pulmonary exacerbation; SAE: serious adverse event

Table 3-2 Study VX19-445-107: Part B Treatment Period and Safety Follow-up Visit

Event/Assessment ^a	Part B Treatment Period (96 weeks)					Part B ETT Visit ^b	Part B Safety Follow-up Visit ^c (28 ± 7 Days After Last Dose of Study Drug)	Comments
	Day 1 ^d	Weeks 4, 8, 16, 20, 28, 32, 40, 44, 52, 56, 64, 68, 76, 80, 88, 92 (± 5 Days)	Weeks 12, 36, 60, 84 (± 5 Days)	Weeks 24, 48, 72 (± 5 Days)	Week 96 (± 5 Days)			
Clinic visit	X		X	X	X	X	X	
Telephone contact		X						When telephone contact takes the place of a clinic visit, a urine pregnancy test will be performed with a home kit provided by the study site (Section 11.5.2).
Part B Informed consent and assent	X							
Inclusion and exclusion criteria confirmation	X							See Section 8 for details.
CFQ-R	X			X	X	X	X	To be completed before any other assessments scheduled at relevant visits (Section 11.3.5).
Ophthalmologic examination					X	X		Subjects will have an ophthalmologic examination at Week 96 (Section 11.5.5). In addition, an ophthalmologic examination will be performed at the ETT Visit for subjects who discontinue study drug if the subject has received at least 12 weeks of study drug since their last ophthalmologic examination.
Full physical examination	X				X	X		Symptom-directed physical examinations will be performed at any time if deemed necessary by the investigator or healthcare provider (Section 11.5.3).
Weight, height, and BMI	X		X	X	X	X	X	Weight and height measured with shoes off (Section 11.3.4).
Vital signs	X		X	X	X	X	X	Performed after subject has been at rest (seated or supine) for at least 5 minutes (Section 11.5.3).

^a All assessments will be performed before study drug dosing unless noted otherwise.

^b If a subject prematurely discontinues study drug treatment, an ETT Visit should be scheduled as soon as possible after the decision to discontinue treatment (Section 9.1.3).

^c The Safety Follow-up Visit is required for all subjects unless otherwise specified. If an ETT Visit occurs 3 weeks or later following the last dose of study drug, then the ETT Visit replaces the Safety Follow-up Visit (Section 9.1.2).

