10.2.2.5 Study Drug Exposure

Study drug exposure summaries will be based on the OLE-SS.

Duration of study drug exposure (in days) will be calculated as [last dose date – first dose date + 1 day] within the OLE Safety Period, regardless of study drug interruption. For subjects who are still on study drug at IA data cutoff date, the corresponding cutoff date will be used as the last dose date for the exposure calculation.

Study drug exposure (in weeks) will be summarized descriptively by the number of subjects (n), mean, SD, median, min, and max. It will also be summarized into the following categories: <=24 weeks, >24 to <=48 weeks, >48 to <=72 weeks, >72 to <=96 weeks, >96 to <=120 weeks, >120 to <=144 weeks, >144 to <=168 weeks, >168 to <=192 weeks, >192 weeks. Additionally, the total study drug exposure, defined as the sum total of the study drug exposure across all subjects (in patient-weeks and patient-years), will be provided.

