11 INTERIM AND DMC ANALYSES

11.1 Interim Analysis

In the protocol it has been mentioned that IA may take place at any time during the study at the discretion of the sponsor to support regulatory and/or reimbursement dossiers. An interim analysis was conducted when the last subject reached Part A Week 24. The analysis details of the Week 24 interim analysis were provided in Section 11.1.1 below. Another IA will be conducted when the last subject reaches Part B Week 48, i.e., Week 144 in the OLE study. The analysis details of the Week 144 IA are provided in Section 11.1.2. Unless specified otherwise, the general rules, principles, and scopes specified in Section 10 apply to the IAs.

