Obtain the age at informed consent in “yy, mm” format (e.g., 24 years, 6 months) in parent study from the VS page at the Screening Visit in the parent study.			
Obtain the informed consent date in parent study.			
Then age (in months) at first dose or post-baseline visit = integer part of {[age at informed consent (in months) in parent study + 0.5 + diff(first dose date or post-baseline visit date, informed consent date) in months in parent study]} + 0.5.			
3. Missing first dose date or last dose date			
If the first dose date is missing, use Day 1 visit date.			
If the last dose date of study drug is not available and there is no data to indicate that the subject discontinued treatment, the data cutoff date will be used instead.			
If the subject discontinued treatment and the last dose date is missing or partial date is reported, the last dose date will be imputed based on, in descending order priority, the Early Treatment Termination (ETT) visit date, last visit date before the Safety Follow-up, or the last study drug administration date from EX SDTM domain, as appropriate. The imputation algorithm will ensure the imputed last dose date does not exceed the data cutoff date.			
4. Electrocardiogram:			
Baseline is defined in Section 8.1. If multiple ECG measurements are obtained on the same calendar day during the TE period,			
○ For summary purpose, the average value will be used as the ECG on that day;			
○ For threshold analysis purpose, all ECG values will be used			

Table 13-2 Analysis Visit Windows for Safety and Efficacy Assessments for the OLE study			
Assessment	Visit¹	Target Study Day	Analysis Visit Window (in study days)²
Safety Assessment			
Serum Chemistry	Baseline	1	defined in section 8.1
Hematology	OLE Part A Week 8	57	[1, 85]
Vital Signs (excluding Weight, Height, BMI, and corresponding z-scores) ³	OLE Part A Week 16	113	(85, 141]
	OLE Part A Week 24	169	(141, 211]
	OLE Part A Week 36	253	(211, 295]
	OLE Part A Week 48	337	(295, 379]
	OLE Part A Week 60	421	(379, 463]
	OLE Part A Week 72	505	(463, 547]
	OLE Part A Week 84	589	(547, 631]
	OLE Part A Week 96	673	(631, 715]
	OLE Part B Week 12	757	(715, 799]
	OLE Part B Week 24	841	(799, 883]
	OLE Part B Week 36	925	(883, 967]
	OLE Part B Week 48	1009	(967, 1051]
	OLE Part B Week 60	1093	(1051, 1135]
	OLE Part B Week 72	1177	(1135, 1219]
	OLE Part B Week 84	1261	(1219, 1303]
	OLE Part B Week 96	1345	(1303, 1359]
	Safety Follow-up ⁴	Not applicable	Use nominal visit

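### At the Week 144 interim analysis, the percentage of tablets taken is biased upward for subjects still on drug, because tablets in hand at the cutoff count as taken

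*SAP*

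**What the plan says.** SAP Section 10.2.2.6 gives two adherence measures for the whole extension study. The first, called study drug compliance, is based on days of interruption. The second is based on tablet counts: the "percentage of tablets taken will be calculated using the following formula", namely 100 × (dispensed − returned) / (planned tablets per day × exposure days). The only deduction in the numerator is the "total number of tablets returned". The tablet measure is to be summarized in a similar way to compliance, which is split at 80%.

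For subjects still on drug at an interim cutoff, SAP Section 10.2.2.5 says that "the corresponding cutoff date will be used as the last dose date for the exposure calculation". SAP Section 11.1 sets the timing ("Another IA will be conducted when the last subject reaches Part B Week 48, i.e., Week 144 in the OLE study") and adds: "Unless specified otherwise, the general rules, principles, and scopes specified in Section 10 apply to the IAs". Section 11.1.2, which covers the Week 144 analysis, gives no different rule for tablet counts.

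In Protocol Table 3-2, Part B clinic visits fall every 12 weeks, with telephone contacts between them. Study drug counts are scheduled only at clinic visits after Day 1 and at the Early Termination of Treatment visit. Protocol Section 9.6.1 has drug dispensed at visits as appropriate, without a quantity, and used and unused materials brought back to the site. It also gives the daily regimen as three tablets.

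**The concern.** Dispensed minus returned equals tablets taken only when every unused tablet has come back. At an interim cutoff that is not so for a subject still on treatment, who holds the supply from the latest dispensing. The denominator stops at the cutoff, but the numerator includes the whole of that supply, part of which is meant for days after the cutoff. While supply remains in hand the error can only be upward.

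At stake is the only planned adherence statistic that uses tablet counts. Protocol Section 10.6 names the drug count as one of the ways compliance is assessed, and SAP Section 11.1 says interim analyses may support regulatory or reimbursement dossiers. A table in that setting could show values above 100%, or place in the upper category a subject whose true value is below 80%.

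**Working it through.** The documents give no adherence figure, so there is nothing to reproduce. The check applies the SAP formula directly.

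**Inputs**
- Planned tablets per day: 3 at both dose levels (Protocol Section 9.6.1). This cancels in the ratio.
- B, exposure days at the last clinic visit: 1009, the target day for Part B Week 48 (SAP Table 13-2). The ±5-day visit window gives 1004 to 1014.
- S, days of supply dispensed at that visit: not stated. Assumed 84 (12 weeks × 7), the interval to the next clinic visit; 28 to 98 days tested.
- t, days from that visit to the cutoff.
- a, true adherence, taken as constant, with all earlier unused tablets returned.

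**Formula**

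Reported = 100 × (3aB + 3S) / (3(B + t))

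Overstatement = reported − 100a = 100 × (S − a·t) / (B + t)

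This is positive as long as t is below S.

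**Cutoff on the dispensing day (t = 0)**
- In tablets: 3 × 84 = 252 in hand and 3 × 1009 = 3027 planned; 252/3027 = 8.3 points.
- Over the visit window: 84/1004 = 8.4 and 84/1014 = 8.3.
- Other supply sizes at Day 1009: 28/1009 = 2.8; 56/1009 = 5.6; 98/1009 = 9.7.
- Later dispensing visits with 84 days' supply: 84/1093 = 7.7; 84/1177 = 7.1; 84/1261 = 6.7.
- If the Day 1009 dose of a fully adherent subject comes from the new supply, the ceiling is (84 − 1)/1009 = 8.2.

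**Cutoff between visits (B = 1009, S = 84)**

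| t (days) | a = 75% | a = 100% |
|---|---|---|
| 0 | 84/1009 = 8.3 | 84/1009 = 8.3 |
| 42 | (84 − 31.5)/1051 = 5.0 | (84 − 42)/1051 = 4.0 |
| 83 | (84 − 62.25)/1092 = 2.0 | (84 − 83)/1092 = 0.1 |

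Averaged over t = 0 to 83, the overstatement is 5.1 points at 75% adherence, 4.5 at 90% and 4.1 at 100%. For intervals starting at Days 1093 to 1261 the averages run from 4.7 down to 3.3.

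**Effect at the 80% cut (84 days' supply, B = 1009)**
- t = 0: a true 75% is reported as 83.3% and a true 100% as 108.3%. True values from 80 − 8.3 = 71.7% up to just under 80% are reported as 80% or more.
- t = 42: the lower limit is (0.80 × 1051 − 84)/1009 = 75.0%.
- t = 83: the lower limit is (0.80 × 1092 − 84)/1009 = 78.3%.

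**After the fix**

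With numerator and denominator both stopped at the Day 1009 count, the ratio is 3a × 1008 / (3 × 1008) = a. A true 75% is reported as 75.0% and a true 100% as 100.0%, apart from lost tablets.

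**The case against.** The best case on the other side concerns size and consequence, and much of it stands.

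- **The supply is unknown.** Dispensing detail is left to the Pharmacy Manual. The 84 days are an inference from the visit schedule, so the result has to be given as a range.
- **8.3 points is a ceiling.** It needs a cutoff on the dispensing day at about Day 1009. The last subject's arrival at Part B Week 48 triggers the analysis, so other ongoing subjects will generally have longer exposure and many will be between visits. Their overstatement is smaller.
- **The measure is secondary and descriptive.** The full analysis and safety sets need only one dose, and no analysis or test uses tablet counts. Interruption-based compliance does not use them either. The protocol-deviation item on compliance below 80% is judged by a review team, and nothing ties it to this percentage.

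A reader might infer that subjects will be moved across the 80% cut, that most subjects will be ongoing, or that the efficacy and safety findings are compromised. The documents support none of these. They give no adherence data and no retention figure; Part B is optional, and the protocol allows transition to commercial drug.

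Two replies do not remove the point. Values above 100% would be noticed in the mean or maximum, but a subject lifted from below 80% to just above it would not. Programmers may count only reconciled supplies, but the SAP does not say so, and doing that alone would reverse the bias: with the denominator still at the cutoff, a fully adherent subject 42 days after Day 1009 would show 1009/1051 = 96.0%. Both parts of the ratio must stop at the same count.

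**Conclusion.** The point holds in limited form. As written, the rule gives an upward-biased percentage of tablets taken at the Week 144 interim analysis for subjects still on drug. This follows from the stated formula and cutoff rule together, and no other section corrects it.

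The size rests on the assumed supply, on constant adherence and on earlier unused tablets having been returned. It should be read as the range above, with the 8.3 points as an upper limit under an 84-day supply. A shift into the upper category is possible only for a subject whose true adherence lies in the band just below 80%, and that band narrows as the interval passes.

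Subjects who have stopped treatment and returned their drug are unaffected, as is the final analysis once drug is returned. A reader might also expect the matching Part A text in Section 10.2.1.6 to need the same change. It has no remaining use: the Week 24 interim analysis is done, and at the Week 144 cutoff no subject will still be in Part A.

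**What to change.** Add to SAP Section 10.2.2.6 only:

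> For subjects on study drug at an interim data cutoff, the percentage of tablets taken will be computed through the last study drug count on or before the cutoff. Tablets dispensed at or after that count are excluded from the numerator, and the denominator runs from the first dose date to the day before that count.

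The formula for the final analysis stays as it is. SAP Section 4 allows revisions by amendment before the Week 144 cutoff date.

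The cost is one sentence and a programming filter. The downside is that adherence between the last count and the cutoff is not described for ongoing subjects, a gap of up to about 12 weeks on the Part B schedule. A footnote to the table should say so.

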10.2.2.7 Important Protocol Deviations

An important protocol deviation (IPD) is a deviation that may significantly affect the completeness, accuracy, or reliability of the study data or that may significantly affect a subject's rights, safety, or well-being. A protocol deviation review team will categorize IPDs according to the protocol deviation plan during the study.

Protocol deviations that should be considered as potential IPDs include, but are not limited to:

- Subject was enrolled in the study despite not satisfying one or more inclusion/exclusion criterion
- Subject was less than 80% compliant with study drug for non-safety reasons
- Subject received prohibited concomitant medications

- Subject received the wrong treatment or incorrect doses

IPDs will be summarized descriptively based on the OLE-FAS. Additionally, IPDs will be provided in an individual subject data listing.

10.3 Efficacy Analysis

10.3.1 Efficacy Analysis for Part A

All efficacy analyses described in this section will be based on the OLE-FAS for Part A, unless otherwise specified. The analysis will include all available measurements through the last scheduled visit in Part A, including measurements after treatment discontinuation.

Continuous endpoints during the parent study will be analyzed using the same mixed-effects model for repeated measures (MMRM) approach as described in the SAP for the parent study. The resulting estimates will be identical to what is available in the final CSR of the parent study. Similarly, continuous endpoints during the OLE efficacy period for part A will be analyzed using a separate MMRM. The results obtained from the parent study and the OLE efficacy period for Part A will be displayed one followed by the other.

There is no multiplicity adjustment.

10.3.1.1 Analysis of Primary Efficacy Variables

Not applicable.

10.3.1.2 Analysis of Secondary Efficacy Variables

10.3.1.2.1 Definition of Variables

Percent predicted FEV₁ (ppFEV₁): the ppFEV₁ value is the ratio of FEV₁ (L) and predicted FEV₁ (L), expressed as a percentage. See [Appendix C](#) for more details.

Sweat chloride (SwCl): the SwCl value for a given visit will be calculated as the mean of the non-missing sweat chloride measurements obtained on the left and right arms at that visit. If one of the two arm measurements at a time point is missing, the other will be used as the mean. A volume ≥ 15 μ L is required for an accurate determination of sweat chloride. Any results reported as having volume < 15 μ L will be considered missing for analysis purposes. Any sweat chloride values reported as < 10 mmol/L or > 160 mmol/L will be considered missing for analysis purposes.

Cystic Fibrosis Questionnaire-Revised (CFQ-R): the CFQ-R^{1,4,6} is a validated CF-specific instrument that measures quality-of-life domains. This study utilizes two different versions of CFQ-R:

- CFQ-R for Children ages 6 to 13
- CFQ-R for Parents/Caregivers

In both versions, specific questions belonging to a domain are scored 1, 2, 3, or 4. The CFQ-R domain score, e.g., physical domain score or respiratory domain score, is defined as a scaled score as follows:

Scaled score for a domain = $100 \times (\text{mean (scores of all questions in the domain)} - 1) / 3$,

where the score from a negatively phrased question is first reversed, i.e., reversed score = 5 – actual score, so that 1 always represents the worst condition and 4 the best condition. The (scaled) domain

score ranges from 0 (worst condition) to 100 (best condition). The scaled score for a specific domain will not be calculated if more than half of the questions in the domain have missing scores.

Body mass index (BMI): the BMI at each visit is calculated using the weight and height at each visit as follows:

$$\text{BMI} = \text{Weight (kg)} / [\text{Height (m)}]^2$$

BMI z-score: the BMI score, adjusted for age and sex, will be referred to as BMI-for-age z-score (BMI z-score). The BMI z-score will be calculated by using Centers for Disease Control and Prevention (CDC) growth charts⁷, with the age (in months) used for the calculation defined in Appendix A.

Height z-score and Weight z-score: the height z-score and weight z-score, adjusted for age and sex, will be referred to as weight-for-age z-score (weight z-score) and height-for-age z-score (height z-score). The weight z-score and height z-score will be calculated by using Centers for Disease Control and Prevention (CDC) growth charts⁷, with the age (in months) used for the calculation defined in Appendix A.

Pulmonary exacerbation (PEx): A PEx is defined as a new or changed antibiotic therapy (intravenous [IV], inhaled, or oral) for any 4 or more of the following signs/symptoms:

- Change in sputum
- New or increased hemoptysis
- Increased cough
- Increased dyspnea
- Malaise, fatigue, or lethargy
- Temperature above 38°C (equivalent to approximately 100.4°F)
- Anorexia or weight loss
- Sinus pain or tenderness
- Change in sinus discharge
- Change in physical examination (PE) of the chest
- Decrease in pulmonary function by 10%
- Radiographic changes indicative of pulmonary infection

The number of PEx is then defined as the total number of PEx during the Cumulative TC Efficacy period.

Lung clearance index (LCI): the LCI assessments are derived from N₂-multiple-breath washout (MBW) testing. Each MBW will be performed in multiple replicates for each visit and the final LCI value will be calculated from the technically acceptable washout replicates as graded and determined by a central reader. The following algorithm is used to derive the LCI values at each visit based on the multiple replicates:

- When there is only one acceptable replicate at the visit, the LCI values will not be calculated. The assessment for that subject at the corresponding visit will be missing.
- Where there are 2 or more acceptable replicates at the visit, the mean of the values for the acceptable replicates will be calculated as the LCI value at the corresponding visit.

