4 INTRODUCTION

This statistical analysis plan (SAP) for Study 445-107 is based on the most recent approved clinical study protocol (CSP), the most recent approved electronic case report form (eCRF), and the most recent approved eCRF completion guidelines.

This SAP (Methods) documents the planned statistical analyses of safety and efficacy endpoints for the study. It also documents analyses for additional safety and efficacy variables not specified in the protocol. PK and PD (if applicable) analyses will be documented separately in the clinical pharmacology analysis plan (CPAP) for the study.

Due to the outbreak of COVID-19, to ensure continued safety of subjects who *cannot* travel to the study sites for their visits (for any reason due to COVID-19), specific alternative measures are being implemented to minimize the risk of exposure to COVID-19. This SAP summarizes the additional statistical analyses that are related to these alternative measures.

The Vertex Biometrics Department or designee will perform the statistical analysis of the safety and efficacy data; SAS (Version 9.4 or higher) will be used to generate all statistical outputs (tables, figures, listings, and datasets).

The SAP (Methods) Version 1.0 was finalized and approved prior to data cutoff for the Week 24 Interim Analysis (IA). SAP Version 1.0 specified analysis details for both the Week 24 IA and the final analysis under CSP Version 1.0. After the Week 24 IA, the CSP Version 1.0 was amended to extend the study treatment period from 96 weeks (under CSP Version 1.0) to 192 weeks (under CSP Version 2.0). Accordingly, the SAP Version 1.0 was amended to Version 2.0 to incorporate study design changes in CSP Version 2.0. This SAP Version 3.0 was amended from SAP Version 2.0 to provide analysis details for a planned Week 144 IA (IA will be conducted based on the Part B Week 48 data cutoff. The safety analysis will be based on pooled Part A and Part B data. This IA will hereafter be called Week 144 IA) and the final analysis. This SAP Version 3.0 will be finalized before the data cutoff date of the Week 144 IA. Any revisions to this approved SAP Version 3.0 will be documented and approved in an amendment to this SAP before the data cutoff date of Week 144 IA.

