7.1 Overall Design

This is a Phase 3, multicenter, open-label extension study for subjects who completed the Treatment Period in the parent study (VX18-445-106 Part B) and meet eligibility criteria.

A schematic of the study design is shown in [Figure 7-1](#).

Study visits and assessments to be conducted are shown in Table 3-1 and Table 3-2 of the CSP. All visits will occur within the windows specified.

Figure 7-1 Schematic of the Study Design

IVA: ivacaftor; TEZ: tezacaftor

Note: The parent study is VX18-445-106 Part B, a Phase 3 study investigating ELX/TEZ/IVA in subjects 6 through 11 years of age. The figure is not drawn to scale.

^a Subjects whose Part B Day 1 Visit is on the same day or within 1 calendar day of the Part A Week 96 Visit do NOT have to repeat any Part B Day 1 assessments that were specified to be performed at the Part A Week 96 Visit. Subjects whose Part B Day 1 Visit is more than 1 calendar day after the Part A Week 96 Visit must complete all assessments specified for the Part A Week 96 AND Part B Day 1 Visits.

All subjects will receive ELX/TEZ/IVA at the weight-appropriate dosage levels for 96 weeks in Part A. In Part B, subjects will receive ELX/TEZ/IVA at age- and weight-appropriate dosage levels for 96 weeks (Table 7-1).

Table 7-1 Treatment Period Dosages

Subject Weight	ELX Dosage	TEZ Dosage	IVA Dosage
Part A, subjects ≥6 years of age			
≥30 kg	200 mg qd	100 mg qd	150 mg q12h
<30 kg	100 mg qd	50 mg qd	75 mg q12h
Part B, subjects ≥6 to <12 years of age			
≥30 kg	200 mg qd	100 mg qd	150 mg q12h
<30 kg	100 mg qd	50 mg qd	75 mg q12h
Part B, subjects ≥12 years of age			
All weights	200 mg qd	100 mg qd	150 mg q12h

IVA: ivacaftor; q12h: every 12 hours; qd: once daily; TEZ: tezacaftor

Note: Study drug administration is described in Section 9.6.

Part A:

Subjects weighing ≥30 kg at the Part A Day 1 Visit will receive 200 mg ELX once daily (qd)/100 mg TEZ qd/150 mg IVA every 12 hours (q12h) for the duration of the study. Subjects weighing <30 kg at the Part A Day 1 Visit will receive 100 mg ELX qd/50 mg TEZ qd/75 mg IVA q12h. If a subject enters the current study weighing <30 kg and subsequently weighs ≥30 kg at 2 consecutive clinic visits, the dose will be adjusted to the higher dose of 200 mg ELX qd/100 mg TEZ qd/150 mg IVA q12h for the remainder of the study, starting with the second visit where subject's weight is ≥30 kg.

Part B:

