7.2 Sample Size

The primary and secondary objectives of the study are the evaluation of the long-term safety, tolerability, and efficacy of ELX/TEZ/IVA. This is an open-label study that will enroll subjects who complete study treatment in the parent study and meet eligibility criteria. Sixty-four subjects enrolled in this open-label study.

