9.3 Analysis Period for Final Analysis

OLE Efficacy Period: Time from the first dose of study drug in the OLE study to the last efficacy assessment, which may be collected up to OLE Part B Week 96 Visit or the earlier of Day 1345 and the end of study participation if subject does not have the OLE Part B Week 96. This analysis period will be used with the OLE-FAS to analyze efficacy data in the Week 144 IA and the final analysis.

OLE Safety Period: Time from the first dose of study drug in the OLE study to 28 days after the last dose of the study drug in the OLE study or to the completion date of study participation (as defined in Section 9.1.5 of the CSP), whichever occurs first.

The completion date of study participation will be obtained from the end of study page of the eCRF.

The **OLE Treatment-emergent (TE) Period** is same as the OLE Safety Period.

The OLE Cumulative TC Efficacy Period: For subjects who enrolled in the OLE study, the time from the first dose of study drug in the parent study (445-106 Part B) until the last efficacy assessment in the OLE study, which may be collected up to the Part B Week 96 Visit or the earlier of Day 1345 and the end of study participation if subject does not have the Part B Week 96 Visit. For subjects who did not enroll in the OLE study and were enrolled and received study drug in the parent study, definition of this analysis period is the same as the parent study efficacy period.

The Cumulative TC Efficacy periods will be used with the Cumulative TC sets for analysis of PEx data.

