10.3.2 Efficacy Analysis for the OLE study

All efficacy analyses described in this section will be based on the OLE-FAS, unless otherwise specified. The analysis will include all available measurements through the last scheduled visit in the OLE study, including measurements after treatment discontinuation.

Continuous endpoints during the parent study will be analyzed using the same mixed-effects model for repeated measures (MMRM) approach as described in the SAP for the parent study. The resulting estimates will be identical to what is available in the final CSR of the parent study. Similarly, continuous endpoints during the OLE efficacy period will also be analyzed using separate MMRM models for Parts A and B, so that Part A data will be analyzed consistently as what was done in the Part A analysis and the resulting estimates will be identical to the Part A analysis results. The results obtained from the parent study and the OLE efficacy period will be displayed one followed by the other.

There is no multiplicity adjustment.

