10.3.2.2 Analysis of Secondary Efficacy Variables

10.3.2.2.1 Definition of Variables

The list of variables and their definitions are identical to Section 10.3.1.2.1

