10.3.2.2.2 Analysis Method

Absolute change in ppFEV₁ from baseline:

For Part A data during the OLE efficacy period, the same model in Section 10.3.1.2.2 will be repeated. For Part B data during the OLE efficacy period, similar MMRM model will be applied based on the OLE-FAS. The model will include absolute change from baseline in ppFEV₁ as the dependent variable, and visit in Part B as the fixed effect, with baseline ppFEV₁ value and genotype group (F/F vs. F/MF) as covariates. The model will be estimated using restricted maximum likelihood. Denominator degrees of freedom for the *F*-test of fixed effects will be estimated using the Kenward-Roger approximation². An unstructured covariance structure will be used to model the within-subject errors. If the model estimation does not converge, a compound symmetry covariance structure will be used instead. Conditional on the observed data and covariates, missing data will be assumed to be missing at random; consequently, no imputation of missing data will be performed.

The estimated mean change from baseline in ppFEV₁ at each post-baseline visit, along with the corresponding 2-sided 95% confidence interval (CI) will be provided.

The analysis will be conducted with the clinic spirometry data only. An additional analysis may also be performed to include pooled spirometry data obtained in clinic and by Air Next Spirometer, if the Air Next Spirometry data are assessed to be reasonably consistent with clinic spirometry data.

Absolute change in sweat chloride from baseline:

Analysis of this PD variable will be based on an MMRM similar to the analysis of the absolute change in ppFEV₁ from baseline with the baseline sweat chloride included as a covariate instead of baseline ppFEV₁.

Absolute change in the CFQ-R respiratory domain score from baseline:

Analysis of this domain (child's version) will be based on an MMRM similar to the analysis of the absolute change in ppFEV₁ from baseline with the baseline CFQ-R respiratory domain score (child's version) included as a covariate instead of baseline ppFEV₁. The analysis will include clinic assessed CFQ-R RD score only. An additional analysis may be performed to include pooled CFQ-R RD score assessed at clinic and at home, if the home assessed data are reasonably consistent with the clinic assessed data.

Absolute change in BMI and BMI-for-age z-score from baseline;

Absolute change in weight and weight-for-age z-score from baseline;

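### Does the 192-week analysis need a rule for child CFQ-R scores once a subject turns 14?

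*SAP*

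**What the plan says.** SAP 10.3.1.2.1 lists two versions of the CFQ-R. One is "CFQ-R for Children ages 6 to 13" and the other is for parents or caregivers; there is no form for ages 14 and over. For the whole extension, SAP 10.3.2.2.1 states: "The list of variables and their definitions are identical to Section 10.3.1.2.1". SAP 10.3.2.2.2 then fixes the modelled score for Part B: "Analysis of this domain (child's version) will be based on an MMRM". SAP 10.3.2 sets the data rule: "The analysis will include all available measurements through the last scheduled visit in the OLE study", and adds that measurements after treatment discontinuation count too.

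On ages and time, SAP 7.1 describes the parent study as "a Phase 3 study investigating ELX/TEZ/IVA in subjects 6 through 11 years of age". SAP 7.2 reports that "Sixty-four subjects enrolled in this open-label study". For a subject without a Part B Week 96 visit, SAP 9.3 ends the efficacy period at "the earlier of Day 1345 and the end of study participation". SAP section 4 records that treatment was lengthened from 96 to 192 weeks by protocol amendment.

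Protocol Table 3-2 schedules the CFQ-R in Part B at Day 1, Weeks 24, 48, 72 and 96, early termination and Safety Follow-up, with no age condition. Protocol 11.3.5 gives one reason for not completing the form, the lack of a validated translation, and says that copies of the forms used are in the Study Reference Manual.

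**The concern.** The age label nearly fitted the 96-week study. After the extension to 192 weeks it no longer does: the oldest entrants pass 14 during Part B, some of them before the Week 144 interim analysis. The definitions were carried over by cross-reference, with no comment on this.

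Two readings then seem possible. Either the child form continues and every score is analysed, or the label acts as a limit and child scores stop at 14. On the second reading, data would go missing by age at the late visits of a secondary endpoint that is plotted to Part B Week 96, and the interval there would widen. On the first, no planned table counts the scores that lie outside the labelled range.

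**Working it through.** **Timeline.** 96 + 96 = 192 weeks, and 192 × 7 + 1 = Day 1345, which matches the Part B Week 96 target day in SAP Table 13-2. In years, 1344 / 365.25 = 3.68.

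**Who passes 14.** A subject who entered the parent study at 11 is at least 11 + 3.68 = 14.68 at Day 1345. This needs no assumption about the age distribution. Measured from extension Day 1, anyone aged 14 − 3.68 = 10.32 or more is 14 or over at Part B Week 96. For Part B Week 48 (extension Week 144) the cut is 14 − 2.76 = 11.24.

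**How many.** The documents give 64 enrolled, but not the age distribution, the length of the parent study or the number entering Part B. Assume entry ages uniform from 6 to under 12, a parent study of 0 or 24 weeks, and all 64 continuing (the maximum). With t the years since parent-study entry, the share aged 14 or over is (12 − (14 − t)) / 6, or 0 if that is negative.

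| Visit | Parent study 0 weeks: share (of 64) | Parent study 24 weeks: share (of 64) |
|---|---|---|
| Part A Week 96 | 0 (0) | 0.050 (3.2) |
| Part B Week 24 | 0.050 (3.2) | 0.127 (8.1) |
| Part B Week 48 | 0.127 (8.1) | 0.203 (13.0) |
| Part B Week 72 | 0.203 (13.0) | 0.280 (17.9) |
| Part B Week 96 | 0.280 (17.9) | 0.357 (22.8) |

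Over the four modelled Part B visits (4 × 64 = 256 scores) this is 42.2 (16.5%) or 61.9 (24.2%).

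The result depends heavily on the assumed ages. With u the uniform share at Week 96 (0.280 or 0.357), a triangular distribution weighted young gives u² = 0.078 or 0.127, that is 5.0 or 8.1 of 64. One weighted old gives 1 − (1 − u)² = 0.482 or 0.586, that is 30.8 or 37.5 of 64. The range is therefore about 5 to 38 of 64.

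**What would follow if the label were used as a cut-off.** Under the uniform assumption, the Week 96 sample would be 64 − 17.9 = 46.1 or 64 − 22.8 = 41.2. The standard error of the Week 96 mean relative to complete data (generalised least squares, compound symmetry, four Part B visits, no age effect) is:

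| Within-subject correlation | Parent study 0 weeks | Parent study 24 weeks |
|---|---|---|
| 0.7 | 1.095 | 1.150 |
| 0.3 | 1.159 | 1.224 |

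For an assumed SD of change of 10, the 95% half-width is 1.96 × 10 / 8 = 2.45 with all 64 scores, and 2.45 × 1.095 to 2.45 × 1.224 = 2.7 to 3.0 under the cut-off. For SD 20 it is 4.90 against 5.4 to 6.0.

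**Whether the plan allows that cut-off.** Three features of the text speak against it.

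1. There is no third form to switch to, and the child form is the one modelled in Part B.
2. All available measurements are included, and the visit schedule carries no age limit.
3. SAP 10.3.1.2.1 says so when it wants a value dropped: sweat volume below 15 µL, sweat chloride below 10 or above 160 mmol/L, a CFQ-R domain with more than half its items missing, and an LCI visit with only one acceptable replicate. Age is not among these exclusions. The ages appear only in the name of the form.

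The widening of 9 to 22% therefore describes a departure from the plan.

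**The case for a change.** The strongest case for a change is that the mismatch is certain for subjects who entered at 11, that it stems from an extension after which these definitions were not revisited, and that a SAP which writes explicit validity limits for sweat chloride and LCI could spare a sentence for a questionnaire used beyond its labelled ages. Fixing the rule in advance also stops the choice being made after the data are seen. The cost is small, because Appendix A already derives age at each post-baseline visit.

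What stands is that the sentence is absent and that no planned table counts scores from subjects aged 14 or over. It does not follow that the rule is open. The explicit limits elsewhere in the section count against an unwritten age limit. Nor is the reader left without information: age at parent-study baseline is summarised (SAP 10.2.2.2), the number of subjects is given by visit (10.3.2.2.2), and the parent-version respiratory score is summarised at each visit (10.3.2.2.5), although none of these isolates subjects aged 14 or over. Whether the child form performs less well at 14 or 15 cannot be judged from these documents, and the Study Reference Manual may already name the form in use.

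**Conclusion.** The observation is correct, but it calls for no change. The plan retains the child form and all its scores, so neither bias nor loss of precision follows from the silence about age 14. The mixed model would be the same with or without a clarifying sentence, as would every estimate and interval. What is missing is a detail that analysts following the text would fill in the same way.

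The number of subjects past the label is uncertain: 18 or 23 of 64 at Part B Week 96 with uniform entry ages and a parent study of 0 or 24 weeks, and about 5 to 38 across the age shapes tried, always with all 64 continuing. The stakes are also limited. The CFQ-R respiratory score is one of several secondary endpoints in a single-arm study whose primary endpoint is safety, with no multiplicity-controlled efficacy testing. Confirming the retention of scores from age 14, or adding a count by visit, would be optional editing.
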